Sample Size Determination. Crossover designs are highly cost-efficient and powerful designs (Wellek and Blettner 2012). Previous research has shown NAC has an effect size of d =1.13 versus placebo on glutamatergic levels in the ACC in cocaine dependent adults in a similar randomized, double-blind, placebo-controlled within-subjects crossover study (Schmaal et al. 2012). With 32 participants, the proposed study will have 85% power to detect such effects (α = 0.05, two-tailed) (Erdfelder et al. 1996). Having 50 heavy drinking participants will allow for 20% participant drop out, which is consistent with the drop out rate at the 4 week mark in [name] NAC adolescent marijuana trial, as well as exclusion of participants due to motion in scanner (Gray et al., 2012).

Analysis and approach. (1) BOLD response to alcohol vs. non-alcohol cues in the regions of interest (ACC, insula, striatum, amygdala) and (2) glutamate levels in the ACC will be the primary contrasts of interest to test Aims 1 and 2. A generalized linear mixed effect model will examine the effect of NAC vs placebo on alcohol cue reactivity and glutamate. The primary model will contain the main effect of treatment (NAC vs. placebo), as well as day (scan 1 vs. scan 2) and order (NAC vs. placebo) to ensure the crossover design and washout period were successful. During model development, random intercepts will be included to account for variations in baseline response levels for individual participants and random slopes to account for varying responses to treatment. Model fit will be tested using likelihood ratio tests and Akaike Information Criterion values. Baseline levels of clinical and demographic characteristics (sex, age, alcohol use characteristics) will be tested for univariate associations with study outcomes; when associated, these variables will be included in the adjusted model development strategy. Parameter estimates and associated 95% confidence intervals for treatment effects on cue reactivity and glutamate will be reported. Model based parameter estimates across groups (means and standard deviations) will be used to estimate treatment effect sizes, in order to inform power analysis for a subsequent full-scale randomized controlled trial. Power analyses and predetermined statistical analyses will ensure findings are robust and unbiased.

We will also analyze the effects of adolescent binge drinking and sex as a biological variable (SABV), as compared to a non-drinking control group (1:1 sex ratio), to assess the alcohol-related effects within (1) glutamate, GABA, and NAA levels in the ACC, (2) BOLD response to alcohol v. non-alcohol cues in the regions of interest (ACC, insula, striatum, amygdala), and (3) microbiome composition. Two-way analysis of variance (ANOVA) will be used to test the main effects of group and SABV, as well as their interaction (group × SABV). Resulting significant interaction terms will be further tested to assess the effect of group within sex (e.g., difference in glutamate levels between drinking and non-drinking females) and the effect of sex within group (e.g., difference in glutamate levels between male and female heavy drinkers). Clinical and demographic characteristics (age, alcohol use characteristics, GM:BM for MRS data) will be tested for univariate associations with study outcomes; when associated, these variables will be included in an analysis of covariance (ANCOVA). Power analyses and predetermined statistical analyses will ensure findings are robust and unbiased. Summary statistics across groups (means and standard deviations) will be used to estimate SABV and alcohol effect sizes, in order to inform power analysis for a subsequent full-scale studies. SAS will be used for data analysis with a significance level of $\alpha = 0.05$, corrected for multiple comparisons.

Biological markers. Changes in blood phosphatidylethanol (PEth), urinary Ethylglucuronide (EtG), and blood inflammatory marker (IL-6, IL-10, IL-1B, HMGB1) levels from pre- to post-treatment will be explored in relation to participants' change in drinking behaviors. This data can be used to inform power analysis for a subsequent full-scale randomized controlled trial.

Interpretation of results and future studies. We believe the proposed study is important and will inform future treatment options for adolescent substance use. Given the promising findings from marijuana-using adolescents (Gray et al. 2012), it is important to examine the effect of NAC on alcohol cue reactivity and glutamatergic systems, as modifying these neural systems via pharmacotherapy could decrease alcohol use during adolescence. However, some limitations exist. We may find that NAC does not affect alcohol cue reactivity or glutamate levels compared to placebo, which in itself would be important information and clarify the underlying mechanism of NAC. Regardless of NAC effects, understanding how varying levels of drinking affect glutamate will be important in informing future targeted therapies. The majority of the preclinical NAC literature was performed on male rodents; sex could play a factor in the response to the treatment and will be explored in analyses, as we will be collecting data on an equal number of male and female participants. NAC has the potential to significantly advance treatment options for adolescent heavy drinkers and could provide a safe, tolerable, accessible, and affordable option for adolescents seeking alcohol treatment.

The long-term goals of this work are to determine if NAC is a promising treatment for adolescent heavy

alcohol use, which is consistent with the trans-NIH initiative to identify neurally-informed novel substance use treatments for adolescents.

Provisions to Monitor the Data to Ensure the Safety of Subjects

- (a) **Trial Management:** All aspects of the study will be run through the MUSC Department of Psychiatry and Behavioral Sciences, where the PI holds her faculty appointment.
- (b) **Data Management and Analysis**: Data will be collected using standardized paper or electronic forms and will only be identified with the study's ID of the participant. The codes linking the name of the participant to the study ID will be kept confidential in a secured cabinet by the PI. Collected forms will be securely transported to the PI's data entry center. Research assistants will enter data in REDCap (Research Electronic Data Capture), a secure, webbased application designed exclusively to support data capture for research studies. REDCap provides: 1) an intuitive interface for data entry (with data validation); 2) audit trails for tracking data manipulation and export procedures; 3) automated export procedures for seamless data downloads to common statistical packages (SPSS, SAS, Stata, R); 4) procedures for importing data from external sources; and 5) advanced features, such as branching logic and calculated fields. These procedures are effective in minimizing data entry errors (e.g., missing or errant data). When possible, participant direct entry into REDCap (rather than paper forms) will be utilized.
- (c) Regulatory Issues: The protocol will be registered on the clinical trials registry (clinicaltrials.gov). All serious adverse events will be reported to the MUSC Institutional Review Board (IRB) within 24 hrs. Follow-up of all serious adverse events will be reported as well. All adverse events are reviewed weekly by the PI and yearly by both the DSMB and the IRB. Any significant actions taken by the local IRB, including significant protocol changes, will be relayed to NIAAA. We anticipate the serious adverse event rate to be extremely low. If monitoring indicates otherwise, we will convene a special meeting of the DSMB.
- (d) **Trial Safety:** The potential risks and benefits and methods to minimize these risks are outlined above. Guidelines have been developed for managing and reporting of adverse events (AEs), including serious adverse events (SAE; defined as any untoward medical occurrence that results in death, is life-threatening, requires or prolongs hospitalization, causes persistent or significant disability/incapacity, results in congenital anomalies/birth defects, or in the opinion of the investigators represents other significant hazards or potentially serious harm to research subjects or others). [name] will serve as the Program Managers for AEs. If an AE is non-serious (self-limited with no intervention needed), no further action will be necessary. However, in the case of a serious, unresolved event, an AE follow-up log will be completed within 24 hours of the start of the SAE. Relevant information will be recorded on SAE Notification Form. The complete report (SAE Notification Form, Concomitant Medication Log, and AE Log) will be reviewed with [name], and [name] will notify the IRB, Data and Safety Monitoring Board (DSMB), and NIH about the

SAE. Additionally, [name] will communicate summary reports of DSMB discussion of the SAE, or any deliberations of IRB regarding the review of the SAE or the trial itself, to NIH. If the event is "Serious, Unexpected and Associated" (an SAE is considered unexpected if it is not described in the Package Insert), [name] will complete Food and Drug Administration (FDA) Form 3500A and will forward it to the FDA with [name] assistance. [name] also will inform the IRB and the study participants (and parents/guardians, as appropriate) about the SAE. In all of these reviews and reports, strict patient confidentiality will be maintained.

AEs will be coded on a weekly basis using Medical Dictionary for Regulatory Activities (MedDRA) rules and entered into a database. For each weekly study meeting, [name] or research staff will prepare a summary of all AEs, including their severity and presumed relation to study medication. [name] will review this at their weekly meetings (or before if more urgent).

Study procedures will follow as much as possible the FDA's Good Clinical Practice Guidelines. We will encourage participants (and parents/guardians as appropriate) to notify their physicians that a) they are in a research study evaluating N-acetylcysteine, and b) the physician should contact the PI directly if the physician has any questions.

The research assistants will be instructed not to reveal whether a person is a participant in the study and will report to the PI any outside requests for information about a participant or any breaches in confidentiality. All requests by participants' physicians and other medical providers will be referred directly to the PI.

- (f) **Trial Efficacy:** The Data and Safety Monitoring Board may request a blinded interim efficacy report (blinded to the PI and research team) for review while the trial is ongoing. Final (fully unblinded) analyses will occur after all participants have completed all visits.
- (g) **Data and Safety Monitoring Plan Administration:** The PI will be responsible for monitoring the trial and will examine the database regularly for missing data, unexpected distributions or responses, and outliers. The PI will prepare the weekly adverse event database immediately prior to the weekly meetings with [name] to a) see if any particular MedDRA categories are being endorsed more frequently than anticipated, and b) determine if any adverse event symptom checklist scores are higher than expected. A DSM report will be filed with the IRB and NIAAA on a yearly basis, unless greater than expected problems occur. The report will include participant characteristics, retention and disposition of study participants, quality assurance issues and reports of adverse events, significant/unexpected adverse events and serious adverse events.

Data and Safety Monitoring Board: We will create a DSMB, comprised of multidisciplinary faculty with expertise in pharmacotherapy and behavioral treatment trials (youth and/or addiction-related). The DSMB will meet annually (more frequently as needed for emergent situations) to review any AEs related to the study, as well as review any data management related errors. The board may be called at any point if needed for serious adverse events, etc. Modification will be made in the procedures and/or the protocol if necessary based on the findings of the board.

Risks to Subjects

Questionnaires and interviews are all non-invasive and, as such, involve minimal physical risk to participants.

In order to address any concerns regarding coercion, adolescents and parents will be informed that they are free to choose not to participate and may withdraw at any time (this is included in the consent and

assent forms). Since this study involves minors, particular caution will be exercised in obtaining informed adolescent assent separately and independently from parental consent. To this end, an initial step in subject recruitment involves obtaining parental/legal guardian permission for participation by the adolescent. Once parental consent is secured, subjects will be asked separately and independently for informed consent (i.e., parental consent will not be used to persuade teens to participate). This approach is considered very effective in minimizing coercion to participate.

Potential risks incurred by participants include:

- 1. Adverse events related to study medication
- 2. Loss of confidentiality
- Adverse events related to MRI

Adverse events related to study medication. *N*-acetylcysteine has a generally benign adverse effect profile. A meta-analysis of studies evaluating long-term oral treatment with *N*-acetylcysteine for prevention of chronic bronchitis found that *N*-acetylcysteine was well tolerated, with generally mild, most commonly gastrointestinal adverse effects that did not require treatment interruption (Grandjean et al. 2000). Our experience to date with *N*-acetylcysteine at the same dose proposed in this trial in youth with cannabis use disorder suggests a benign adverse event profile (Gray et al. 2012).

Some patients who have taken intravenous *N*-acetylcysteine for the treatment of acetaminophen overdose have had more serious reactions. Allergic reactions have occurred in about 5% of patients taking intravenous *N*-acetylcysteine (Bailey & McGuigan 1998). These reactions may be mild, consisting of flushing, rash, and itching. Less common side effects include trouble breathing, low or high blood pressure, fever, and hives. If untreated, such a reaction could lead to death. Even more rare serious side effects of intravenous *N*-acetylcysteine are irritability, confusion, and seizures. These reactions (severe allergic reaction or seizures) have never been reported when *N*-acetylcysteine is taken orally, as it will be in this study. As a precaution, we will exclude individuals with a recent history of asthma, as they are believed to possess a higher risk of allergic reaction to *N*-acetylcysteine. We will also exclude individuals with a history of seizure disorder.

Loss of confidentiality. Any communication of personal information carries the potential risk of breach of confidentiality.

Adverse events related to MRI. Risks associated with MRI (including fMRI) are minimal for individuals who do not have metal and are not claustrophobic. Some discomfort may result from lying in the scanner for up to 60 minutes.

Procedures for protecting against potential risks

Adverse events related to study medication. The informed consent process will be used to thoroughly educate participants and parents/guardians about potential medication-related risks, including adverse events. This discussion will include thorough review of adverse events associated with oral NAC treatment. Rigorous screening procedures and strict exclusion criteria are designed to exclude potential participants at elevated risk for adverse events. [name] will conduct serial adverse events monitoring as part of medication management. Participants and parents/guardians will have access to the study medical clinician 24 hours, 7 days a week for emergencies. Participants experiencing intolerable adverse events will have the opportunity to reduce dose or discontinue medication altogether, while remaining in the study for ongoing monitoring. Primary mentor [name] has full hospital admitting privileges in the event of an adverse event requiring hospitalization. Urine pregnancy tests will be conducted for female participants.

Adverse events related to confidentiality. Participants will be assured that all records will be kept confidential in research files located in a locked office and entered into a password-protected computer located behind a secure and maintained firewall. Breach of confidentiality is highly unlikely because all personally identifying information will be kept separate from data collected and will be linked only by a master subject identification list which is maintained by the PI.

Adverse events related to MRI. Participants will be told about the potential discomforts associated with lying in the scanner and their heads and necks will be supported for maximum comfort. Earplugs and headphones will be provided to reduce the noise of the scanner to a safe decibel range. Pregnancy testing with immediate results will ensure that no pregnant adolescent receives an MRI. Any positive pregnancy test results would be discussed with the adolescent, and counseling will be provided should the participant indicate distress concerning the result.

Ensuring professional intervention in the event of adverse effects: If a participant should become uncomfortable with any procedures, he/she can withdraw from the study at any time. If any medical problems arise, 911 will be phoned immediately. If psychological distress, suicidal ideation, or another problem should occur, the clinically-licensed PI or a designated backup licensed professional will be contacted immediately. Paperwork detailing the appropriate steps to handling suicidal/homicidal ideation or abuse/neglect cases is posted above every research assistant's phone, along with contact numbers of the PI and Co-Is.

Policy on neuroimaging data: Participants and their family (for those under age 18) are informed that this is a research study and therefore does not include clinical imaging to confirm clinical findings. Therefore, we cannot provide them with medical reports. If the research staff note a structural irregularity on a scan, a neuroradiologist will review it (fully de-identified) and note if it is of clinical significance or not. If the finding has the potential of clinical significance, the volunteer or parents (depending on age) will be notified to follow up with his or her doctor. There is a minimal risk of undue stress or concern if the finding is determined to be benign or not clinically significant. Furthermore, there may be costs associated with the recommended evaluations which are not covered by our research protocol. We include the following in the consent: "If the possibility of such a situation is too stressful for you, your child should not participate in our study."

Potential Benefits to Subjects or Others

Potential benefits of the research to subjects and others: Participation in this study involves minimal risk for participants. Benefits of participation include providing substantial long-term benefits toward understanding the extent to which NAC can affect underlying neural circuitry during adolescence and alcohol use.

Why risks to subjects are reasonable in relation to anticipated benefits: Given the minimal risks to participants involved, we believe the risk/benefit ratio is acceptable. Youth in the study may decrease their alcohol use which could positively affect other aspects of their lives.

References

- Abdelmegeed, M. A., Banerjee, A., Jang, S., Yoo, S.H., Yun, J.W., Gonzalez, F. J., Keshavarzian, A., Song, B. J. (2013) CYP2E1 potentiates binge alcohol-induced gut leakiness, steatohepatitis, and apoptosis. Free Radical Biology and Medicine, 65, 1238–1245.
- Achenbach TM (1991) Manual for the Child Behavior Checklist/ 4-18 and 1991 Profile. University of Vermont, Department of Psychiatry, Burlington, VT
- American Psychiatric Association (2013) Diagnostic and statistical manual of mental disorders (5th ed.). American Psychiatric Publishing, Arlington, VA

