Rationale for vulnerable populations (children and alcohol users). 45 participants in the alcohol-using group will be between the ages of 15 and 19 and heavy alcohol users. We will include one control group of 10 non-alcohol using youth between the ages of 15-19 to test the effect of NAC on glutamate levels in non-alcohol users. We will also include a second control group of 30 non-alcohol using youth

and a second alcohol using group of 20 youth between the ages of 15-19 who will only complete baseline assessments to investigate potential neural and microbiome differences within binge drinking adolescents as compared to non-drinking controls. Creation of alcohol-focused interventions during adolescence could have substantial long-term implications by reducing acute and long-term negative social, academic, and cognitive consequences related to heavy teen drinking and by reducing the rate of youth transitioning from heavy drinking to more problematic alcohol dependence. While participants in this study are not treatment seeking, all participants will be given treatment referrals at the conclusion of the study.

Diverse Population: In this cohort, approximately 50% of the participants will be female, and we aim to recruit participants to approximate the racial and ethnic composition of Charleston County.

Number of Subjects

We will recruit 105 15-19 year-olds (50% female).

Setting

Visits will take place at MUSC in the Institute of Psychiatry and the Biomedical Imaging MRI research facility at [name] (for those visits requiring an MRI). If a participant is unable to attend or complete a visit due to unexpected conflict (e.g., transportation issues, travel, University closings), arrangements may be made to remotely complete as much of the visit procedures as possible to maintain data collection and study engagement.

Recruitment Methods

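### The stated 85% power at 32 participants for d = 1.13 does not fit the crossover design, and the planned number of heavy drinkers is 50 in one place and 45 in another

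*Combined protocol and SAP*

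**What the plan says.** The protocol (combined document of October 2021), under Data Management, Sample Size Determination, takes from a crossover study in cocaine-dependent adults an "effect size of d =1.13 versus placebo on glutamatergic levels in the ACC". At a two-tailed alpha of 0.05 it then states: "With 32 participants, the proposed study will have 85% power to detect such effects". The test, the SD that standardises 1.13 and the correlation between a participant's two scans are not given.

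The same section continues: "Having 50 heavy drinking participants will allow for 20% participant drop out", "as well as exclusion of participants due to motion in scanner".

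The Rationale for vulnerable populations paragraph gives another number: "45 participants in the alcohol-using group will be between the ages of 15 and 19 and heavy alcohol users". It adds to the treatment part: "We will include one control group of 10 non-alcohol using youth". It also lists 30 further controls and 20 further drinkers who complete baseline only. The Specific Aims and the Study Design Overview put 55 participants in the crossover. Number of Subjects says: "We will recruit 105 15-19 year-olds (50% female").

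Under Interpretation of results, the protocol says: "We may find that NAC does not affect alcohol cue reactivity or glutamate levels compared to placebo, which in itself would be important information".

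**The concern.** Each treated participant receives both NAC and placebo, so the treatment effect is estimated within person. A standardised effect as large as 1.13 tested within 32 people should give power close to 1, and 85% is the sort of figure a comparison of two separate groups would give. If so, the one power figure in the documents describes a different design.

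Two things depend on it. First, the protocol attaches importance to a null finding and intends the results to inform the power analysis of a full-scale trial. A reader told that the study has 85% power for 1.13 would think it only just sensitive to a very large effect, when it can detect an effect about half that size on the difference scale. Second, the attrition allowance is built on 50 heavy drinkers. If the crossover group is 45, the room left for scanner-motion exclusions is smaller than stated.

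**Working it through.** **Inputs.** From Sample Size Determination: d = 1.13, N = 32, two-sided alpha 0.05, stated power 85%, 50 heavy drinkers, 20% dropout. From Rationale for vulnerable populations: 45 drinkers and 10 controls in the crossover, 30 controls and 20 drinkers at baseline only. Stated totals: 55 and 105. The within-person correlation ρ is not given, so its whole range is examined.

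**1. Attempt to reproduce 85%.** For a paired t-test the standardised effect on the difference scale is d_z = d / √(2(1 − ρ)), and the noncentrality is d_z√N. At ρ = 0, d_z = 1.13/√2 = 0.799 and the noncentrality is 0.799 × √32 = 4.52. Power from the noncentral t distribution with 31 df, and with 30 df to allow for a period term:

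| Scale of 1.13 | d_z | Power, 31 df | Power, 30 df |
|---|---|---|---|
| SD of differences (same as between-person SD, ρ = 0.5) | 1.130 | >99.99% | >99.99% |
| Between-person SD, ρ = 0.25 | 0.923 | 99.9% | 99.9% |
| Between-person SD, ρ = 0 | 0.799 | 99.2% | 99.2% |
| Between-person SD, ρ = −0.5 | 0.652 | 94.7% | 94.6% |
| Between-person SD, ρ = −1 | 0.565 | 87.2% | 87.1% |

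To get exactly 85% with 31 df, d_z must be 0.547. That implies ρ = 1 − (1.13/0.547)²/2 = −1.13, which is impossible. The figure is not reproduced.

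**2. Other tests.** A signed-rank test at its minimum efficiency of 0.864 can be approximated by an effective sample of 32 × 0.864 = 27.6. It gives 98.1% at ρ = 0, 86.4% at ρ = −0.75 and 81.7% at ρ = −1. It therefore passes through 85%, but only at strongly negative correlations.

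**3. Two independent groups.** With noncentrality 1.13√(n/2), 15 per group gives 84.8% and 16 per group gives 87.1%. So 32 is the smallest equal-group total that reaches 85%. This is a plausible origin of the figure, but the protocol does not say so and it remains an inference.

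**4. What 32 completers can detect.** At 85% power the detectable effect is 0.55 SD of the within-person differences. In between-person SDs this is 0.547 × √(2(1 − ρ)): 0.77 at ρ = 0, 0.67 at ρ = 0.25 and 0.55 at ρ = 0.5. The 95% confidence interval has half-width 2.040/√32 = 0.36 SD of the differences.

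**5. Head counts.**
- With 45: 45 + 10 = 55, and 45 + 10 + 30 + 20 = 105. Both totals match.
- With 50: 50 + 10 = 60, and 50 + 10 + 30 + 20 = 110. Neither matches.
- The 20 baseline-only drinkers do not explain the gap, since 45 + 20 = 65.

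**6. Attrition margin.** 50 × 0.8 = 40, which is 8 above 32 (8/40 = 20%). 45 × 0.8 = 36, which is 4 above 32 (4/36 = 11%). As an illustration only, the SAP (Aim 2, outliers and excluded observations) removes 4 of 31, or 12.9%, for motion and missing baseline cue data together. At that rate 40 × 27/31 = 34.8 and 36 × 27/31 = 31.4 would remain. The share due to motion alone is not stated.

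**The case against.** The strongest reply is that the power statement is under-specified rather than wrong. A two-period crossover can be analysed by comparing period differences between the two sequences, 16 against 16 with 30 df. If 1.13 were the standardised effect of that contrast, power would be 87.1% and 32 would be the smallest balanced total reaching 85%. But that contrast is twice the mean treatment difference over the SD of the differences, which is not a usual way to report d, and it still gives 87%, not 85%. The reading cannot be excluded as the origin of 32, but it does not rescue the stated power.

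It is also fair to say that:
- **The error is conservative.** Enrolment does not hang on it, because the SAP already reports the achieved samples (31 for glutamate, 27 complete for cue reactivity). This stands.
- **Confidence intervals will show what a null excludes.** They are planned, and they do limit the harm. They do not correct the sentence.
- **32 is not a real floor.** For d = 1.13 a paired t-test needs only 17 participants at ρ = 0, so falling somewhat below 32 does no damage for glutamate. For cue reactivity no effect size is stated. This stands: the smaller margin shows an inconsistency in the plan, not a demonstrated loss of power.
- **The 12.9% rate is weak evidence.** It pools two reasons for removal, and the SAP also plans an imputed analysis of all 31. The verdict does not rest on it.

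**Conclusion.** Both parts hold, and the point is minor. For a paired or crossover t-test with 32 participants, d = 1.13 and two-sided alpha 0.05, power is 99.2% or more at any non-negative correlation and never below 87% at any admissible one, against the stated 85%. This covers both usual standardisers of d. It does not cover every possible test, but a signed-rank test would reach 85% only at a correlation between −0.75 and −1.

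Independently, the 50 heavy drinkers in the sample-size section contradict the 45 in the population section, and the protocol's own totals support 45. The margin over 32 after 20% dropout is halved, from 8 to 4. The motion part of that margin concerns only the cue-reactivity analysis; the SAP's quality exclusions for glutamate are linewidth and signal-to-noise ratio.

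**What to change.** In Sample Size Determination, replace the power sentence with wording such as:

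> With 32 completers the crossover has 85% power (paired t-test, two-sided alpha 0.05, single test) to detect a mean within-person difference of 0.55 SD of the within-person differences. For the cited d of 1.13, power exceeds 99% (on the difference scale, or on the between-person SD with a non-negative correlation).

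State which SD standardises 1.13 and any correlation assumed. When reporting results, keep in mind that this sentence describes 32 completers: for the same 0.547 SD difference, paired-t power is about 84% at 31 and 78% at 27.

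Separately, change 50 to 45 to agree with the population section and the totals. Restate the allowance as 36 remaining after 20% dropout, 4 above 32, and say that the motion part applies to the cue-reactivity analysis.

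The cost is wording only. Neither enrolment nor the analysis changes.
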